## 5 Study Methods

### 5.1 General Study Design and Plan

We will conduct a 36-week pragmatic trial in a cohort of cLBP patients (see Figure 1 and Figure 2). The proposed SMART will consist of a 4-week run-in period using an online cognitive-behavioral self-management intervention (PainGuide), followed by two 8-week treatment periods. All participants will be followed for a total of approximately nine months.

At baseline (T1), approximately 500 patients will undergo a comprehensive baseline phenotyping assessment. After receiving PainGuide (access to an online self-management program) for 4 weeks, each participant will complete a light phenotyping assessment (T2) and a subset of these patients (n=160) will complete an additional deep phenotyping assessment. Those who still have significant pain interference ( $\geq 2$  from Patient Global Impression Scale, PGIC) will be randomized to one of the four 8-week long interventions (i.e., Mindfulness-Based Stress Reduction (MBSR), Physical Therapy (PT)/Exercise, Acupressure self-management [eHealth app], or Duloxetine). Participants with a PGIC=1 will not be randomized and continue with long-term follow-up. The PainGuide run-in is designed to provide the lightest “touch” intervention and to help control for regression to the mean. We will use block randomization with random block size of 4 and 8. Approximately 102 patients will be assigned to each treatment group including Physical Therapy/Exercise, MBSR, Acupressure, and Duloxetine treatment groups. For addition details, please see Section 6.3.

Following the first 8-week treatment period, patients will be reassessed (T3) using light only or light plus deep assessments (for the subset of 160) and those still having significant pain interference ( $\geq 2$  from Patient Global Impression Scale [PGIC]) will be re-randomized to receive one of the three treatments they did not receive in the first treatment period. Participants with a PGIC=1 will not be randomized and continue with long-term follow-up. After the second intervention and three months later, all undergo the light phenotyping follow-up assessment protocol (T4). Lastly, a final assessment will take place at 3 months after the scheduled end of the second 8-week treatment period (T5). There will also be a series of interim assessments that take place at 2-week intervals in between the regular assessments (T1-T5).

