## 7.3 Covariates and Subgroups

Since the purpose of the study is to identify patient subgroups that differentially respond to the four treatments, our analysis will explore many treatment-covariate interactions. Table 2 and 3 list the expected treatment modifiers, which are the primary covariates of interest, for the light and deep phenotype measures, respectively. The light phenotype table also describes each variable's expected mechanistic role (treatment modifier versus treatment mediator). For additional details, please see Section 18.1 of the UM BACPAC clinical trial protocol.

Table 2 Hypothesized light-phenotyping treatment modifiers.

Phenotypic variable	Expected treatment-phenotype interaction	Mechanistic Role
Patient pain catastrophizing score	MBSR	Moderator
Patient experience score	MBSR	Mediator
Fear avoidance beliefs score	PT/Exercise	Mediator
PROMIS self-efficacy score	PT/Exercise	Moderator
Fibromyalgia Screening Questionnaire	Acupressure	Moderator
Biologic Sex	Acupressure	Moderator
Fibromyalgia Screening Questionnaire	Duloxetine	Moderator
PainDETECT score	Duloxetine	Moderator

Table 3 Hypothesized deep-phenotyping treatment modifiers.

Deep Phenotype variable	Measurement Modality	Expected treatment-phenotype interaction	Mechanistic Role
Subgenual ACC activity	fMRI	MBSR	Moderator
Ventrolateral PFC activity	fMRI	MBSR	Moderator
S1 activity	fMRI	MBSR	Moderator
Thalamus activity	fMRI	MBSR	Moderator
Baseline activity	Actigraphy	PT/Exercise	Moderator
Parasympathetic tone	Heart Rate Variability	PT/Exercise	Moderator
Vagal Tone	EKG and PPG	PT/Exercise	Mediator

High Basal Inflammation	Blood Sample	PT/Exercise	Moderator
Pain Threshold	QST	Acupressure	Moderator
Posterior Insula Glutamate	H-MRS	Acupressure	Moderator
Insula-DMN connectivity	fMRI	Acupressure	Moderator
DMN-SI connectivity	fMRI	Acupressure	Moderator
Deficient Lower Back Pain Inhibition	QST	Duloxetine	Moderator
Lesser PAG-Insula connectivity	fMRI	Duloxetine	Moderator
Elevated Stimulated inflammatory response	Blood Sample	Duloxetine	Moderator

We plan to conduct a single subgroup analysis that will assess whether males and females differentially respond to the proposed treatments.

In addition to the covariates listed above, the following biological variables will be controlled for in the primary analysis: sex, age, BMI, race, and education.

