#### 9.1.1 Light Phenotyping Analysis

Let  $Y_{ti} \in \mathbb{R}$  denote subject  $i$ 's PROMIS pain interference score at time  $t \in \{2, 3, 4\}$ . Let  $R_i$  denote response status at T3. Let  $A_{ti}$  be a vector denoting treatment assignment, such that the first through 4th elements represent PT/Exercise, MSBR, Acupressure, and Duloxetine treatment status. The vector  $X_{2i}$  contains the baseline covariates for subject  $i$  at time 2 (sex, age, BMI, race, and education) and  $Y_{2i}$ . For  $t \in \{2, 3\}$ , the matrix  $Z_{ti}$  will hold subject  $i$ 's time  $t$  measurements of the hypothesized treatment modifiers.  $Z_{ti}$  will have 7 total columns that correspond to the hypothesized treatment modifiers, and the columns will be specified such that the element-wise product  $A_{ti} \cdot Z_{ti}$  represents the 8 hypothesized treatment-phenotype interactions.

We jointly model data at T3 and T4 to gain efficiency in estimating the main effects of treatment, the main effects of the potential moderators, and the interaction effects between treatment and the potential moderators in stage 1. The main effects of treatment and covariates are allowed to differ between stages, but we assume these effects are additive. In contrast, treatment-by-phenotype interaction effects are assumed to be the same across both stages. We propose the following model:

$$\begin{aligned} E[Y_{3i}] &= X_{2i}^T \beta_2 + A_{2i}^T \phi_2 + Z_{2i}^T \varphi_2 + (A_{2i} \circ Z_{2i})^T \psi_2 \\ E[Y_{4i}] &= X_{2i}^T \beta_2 + A_{3i}^T \phi_2 + Z_{3i}^T \varphi_2 + R_i^T [A_{3i}^T \phi_{3R} + Z_{3i}^T \varphi_{3R}] \\ &\quad + (1 - R_i)^T [A_{3i}^T \phi_{3NR} + Z_{3i}^T \varphi_{3NR}] + (A_{3i} \circ Z_{3i})^T \psi_2 \end{aligned}$$

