We will fit the model for all repeated measures ( $Y_{3i}, Y_{4i}$ ) using generalized estimating equations (GEE) with a working independence covariance matrix through the R package *gee*. We will use robust standard errors for variance estimation to account for the use of repeated measures. Prior to conducting inference, we will assess the functional forms of the predictors and the validity of the assumptions required for joint stage modeling, especially the assumption of constant interaction effects across treatment stages. If the assumptions for joint modeling are violated, we will conduct the primary analysis with stage 1 data only. For inference, we additionally assume  $Y_{3i}, Y_{4i}$  follow a multivariate normal distribution.

The clinical objective of Aim 1 is to show that patient responsiveness to treatment depends on their

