### 9.1.2 Deep Phenotyping Analysis

A second analysis will assess whether deep-phenotyping measures are also predictive of differential treatment response. The form of the model will be nearly identical to the light phenotype-based primary analysis above. The analytic plan and strategy for performing inference on model parameters is the same as stated above in 9.1.1. The primary difference between the primary and secondary analysis is the number of treatment modifiers that were proposed by investigators. As a result, the deep phenotyping-based model will include multiple treatment-phenotype interaction terms for each treatment arm (see Table 5). *Table 5 Hypothesized differential responses to treatment*

Deep Phenotype variable	Measurement Modality	Expected treatment-phenotype interaction	Mechanistic Role
Subgenual ACC activity	fMRI	MBSR	Moderator
Ventrolateral PFC activity	fMRI	MBSR	Moderator
S1 activity	fMRI	MBSR	Moderator
Thalamus activity	fMRI	MBSR	Moderator
Baseline activity	Actigraphy	PT/Exercise	Moderator
Parasympathetic tone	Heart Rate Variability	PT/Exercise	Moderator
Vagal Tone	ECG and PPG	PT/Exercise	Mediator
High Basal Inflammation	Blood Sample	PT/Exercise	Moderator
Pain Threshold	QST	Acupressure	Moderator
Posterior Insula Glutamate	H-MRS	Acupressure	Moderator
Insula-DMN connectivity	fMRI	Acupressure	Moderator
DMN-SI connectivity	fMRI	Acupressure	Moderator
Deficient Lower Back Pain Inhibition	QST	Duloxetine	Moderator
Lesser PAG-Insula connectivity	fMRI	Duloxetine	Moderator
Elevated Stimulated inflammatory response	Blood Sample	Duloxetine	Moderator

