## 9.2 Objective 2 Analysis Plan

**Objective 2:** Identify additional predictors of differential treatment response using light phenotype data.

This exploratory analysis will assess whether additional patient reported outcomes captured in clinical settings can improve the prediction of differential treatment response. First, we will assess the functional forms of the predictors through univariate summaries and assess multicollinearity through pairwise Spearman correlation coefficients. Then, we will fit regularized regression models for the primary pain outcome (PROMIS pain interference score) using observations from time points T3 and T4. We will utilize adaptive elastic net (AENET) to induce variable selection while accommodating groups of correlated predictors. Given the exploratory nature of this objective, that

trial patients may have just failed other treatments prior to entering the study, and the need for as much data as possible for the proposed methods, we will treat observations from time points T3 and T4 as independent rather than as repeated measures and adjust for potential effects of stage 1 treatment on observations at T4. We will consider the selection of a treatment interaction into the model as weak evidence for treatment effect modification, and we will conduct hypothesis testing for strong evidence of treatment effect modification. The analysis will be repeated for the secondary pain outcomes (Pain Intensity (PEG) and Patient Global Impression of Change (PGIC)).

Let  $Y_{ti} \in \mathbb{R}$  denote subject  $i$ 's PROMIS pain interference score at time  $t \in \{2, 3, 4\}$ ,  $R_i$  denote response status at T3,  $A_{ti}$  be a vector denoting treatment assignment for  $t \in \{2, 3\}$ , and  $X_{2i}$  denote the vector of baseline variables for subject  $i$  at time point T2 (sex, age, BMI, race, education, and the baseline outcome). Let  $Z_{ti}$  be a vector denoting the additional (clinical/patient reported) predictors and their treatment interactions for subject  $i$  and  $t \in \{2, 3\}$ . We assume

$$E[Y_{ti}] = X_{2i}^T \beta + A_{(t-1)i}^T \phi + I(t = 4) * [R_i A_{2i}^T \varphi_R + (1 - R_i) A_{2i}^T \varphi_{NR}] + Z_{(t-1)i}^T \gamma,$$

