### 11 Other Analyses

Exploratory, we will analyze the 12 embedded dynamic treatment regimens within the SMART design using the joint model described in section 10.1.1. Additionally, we will consider further tailoring of the embedded dynamic treatment regimens using augmented outcome-weighted learning.

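### The primary joint model leaves stage-1 treatment out of its T4 equation (SAP 9.1.1)

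*SAP*

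**What the plan says.** SAP 9.1.1 fits one GEE model to the T3 and T4 scores. The T3 equation contains A2, the stage-1 assignment. The T4 equation starts "E[Y_{4i}] &= X_{2i}^T \beta_2 + A_{3i}^T \phi_2 + Z_{3i}^T \varphi_2 + R_i^T [A_{3i}^T \phi_{3R} + Z_{3i}^T \varphi_{3R" and continues with a non-responder bracket and the interaction term. Its four treatment terms (`phi_2`, `phi_3R`, `phi_3NR` and the interactions `psi_2`) all carry A3.

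The text adds that "The main effects of treatment and covariates are allowed to differ between stages", while the interactions are held constant across stages. If this fails, "If the assumptions for joint modeling are violated, we will conduct the primary analysis with stage 1 data only".

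Other sections bear on the point:

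- SAP 9.2 fits a similar T3 and T4 model but puts A2 in both response-status brackets, to "adjust for potential effects of stage 1 treatment on observations at T4".
- SAP 5.1, on T3 responders: "Participants with a PGIC=1 will not be randomized and continue with long-term follow-up". SAP 7.2.1 counts such patients as being on long-term follow-up, which is not one of the four elements of A.
- SAP 7.3: "the following biological variables will be controlled for in the primary analysis: sex, age, BMI, race, and education". Table 2 in the same section also lists sex as a modifier.
- SAP 9.1.2, on deep phenotyping: "The form of the model will be nearly identical to the light phenotype-based primary analysis above".
- SAP 11: "we will analyze the 12 embedded dynamic treatment regimens within the SMART design using the joint model described in section 10.1.1".

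**The concern.** In a two-stage design the T4 outcome can reflect both treatments. The SAP accepts this in its exploratory model (9.2) but makes no such adjustment in its primary one. Protocol 9.4 gives one concrete route for carry-over: participants may stay on duloxetine outside the study after the eight weeks.

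Three things are at stake. The printed equation cannot be fitted without unplanned decisions about which columns to drop. Lasting stage-1 effects leak into the stage-2 treatment contrasts. And the only model named for the 12 regimens cannot directly distinguish regimens that differ in their first treatment but share the second.

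**Working it through.** **Pathways.** Four responder pathways plus 4 × 3 non-responder pathways make 16, and 4 × 3 = 12 regimens, which matches SAP 7.5. The printed T4 equation separates only five treatment levels: one for all responders and four for non-responders. At fixed X2 and Z3, the three regimens ending in the same second treatment therefore share one non-responder T4 mean.

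**Rank.** Take race and education as one column each, and A3 = 0 for responders (SAP 5.1 and 7.2.1).

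- Columns: X2 6 + A 4 + Z 7 + A×Z 8 + R×A3 4 + R×Z3 7 + (1−R)×A3 4 + (1−R)×Z3 7 = 47.
- Four R×A3 columns are zero for everyone, and sex is duplicated in X2 and Z. Rank = 47 − 5 = 42, confirmed numerically.
- `psi_2` stays estimable once the five columns are dropped.

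**Stage-2 contrast.** A non-responder never repeats the first treatment. With even allocation, patients on second treatment k had first treatments spread equally over the other three arms. Let s be the stage-1 effects and c the share persisting to T4. The mean carry-over in group k is c(S − s_k)/3, where S is the sum over the four arms. The contrast of k with l therefore shifts by −c(s_k − s_l)/3. With a 0.30 SD difference this is 0.05 at c = 0.5 and 0.10 at c = 1.

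Simulation settings (assumed except for the 408 patients, 7 modifiers and 8 interactions): 15% responders chosen on T2–T3 change, interactions of 0.25 per SD, T3–T4 residual correlation 0.5, least squares with patient-clustered standard errors (equivalent to working-independence GEE), 300–400 replicates.

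| Stage-2 contrast | c = 0 | c = 0.5 | c = 1 |
|---|---|---|---|
| True 0.30, stage effects agree: printed form | 0.31 | 0.26 | 0.21 |
| Same, A2 added | 0.30 | 0.30 | 0.30 |
| True −0.30, stage effects opposite: printed form | −0.29 | −0.34 | −0.39 |
| Same, A2 added | −0.30 | −0.30 | −0.30 |

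Repeat runs of the first row with separate code gave 0.26–0.28 and 0.21–0.23 at c = 0.5 and 1. On the score scale, an assumed lasting 3-point duloxetine effect with no true stage-2 differences implies a false contrast of 3/3 = 1.00 point. Simulation gave 1.02, against 0.04 with A2 added.

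**Regimens sharing a second treatment**, averaged over R and Z3. The columns vary how far stage 1 also moves Z3, as a multiple of the stage-1 effect.

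| Difference (SD) | Z3 × 0 | Z3 × 0.5 | Z3 × 1 |
|---|---|---|---|
| c = 0.5: truth | 0.17 | 0.23 | 0.30 |
| printed form | 0.02–0.05 | 0.08–0.11 | 0.15–0.17 |
| A2 added | 0.18 | 0.24 | 0.31 |
| c = 1: truth | 0.32 | 0.38 | 0.45 |
| printed form | 0.02–0.06 | 0.09–0.12 | 0.16–0.18 |
| A2 added | 0.33 | 0.39 | 0.46 |

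**Tested interactions.** If only main effects persist, `psi_2` is estimated at 100% of truth. If the interaction itself persists by 50% or 100%, the printed form gives 95% or 90%. Responder shares of 10% and 30% give 95–96% and 90–92%. Adding A2 alone leaves these ratios unchanged; adding A2×Z2 as well gives 99% throughout. The false-positive rate is about 6% in all forms.

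**The case against.** **The primary test is barely touched.** This stands. Endpoints are T2–T3 changes, T4 is pooled for efficiency, and adding A2 does not change `psi_2`. Stage-2 contrasts are not a listed endpoint. SAP 11 calls the regimen analysis exploratory, although SAP 5.1 lists regimen comparison as secondary.

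**The size is assumed.** Also true. The documents give no carry-over, stage-1 difference or T3 responder share. The stage-2 bias of 0.05–0.10 SD is below the contrast's standard error of 0.152. The formula assumes even allocation, which eligibility limits (Protocol 8.1) may disturb.

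**The rank deficit depends on coding.** Partly. SAP 9.1.1 does not state A3 for responders. Carrying A2 forward for them would leave only the duplicated sex term. The non-responder bracket would still lack A2. A subscript misread from the PDF is possible but unlikely, since A3 is consistent in all four terms.

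**The fallback covers it.** Only for the primary analysis. The check it singles out is constant interactions, not carry-over. Using it would cut simulated power per interaction from 83% to 52%, and it does not say what SAP 11 would then use.

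**Why not simply substitute A2 for A3, as in 9.2?** Substitution does remove the empty columns and is harmless when stage effects agree. But it forces equal main effects in both stages, which 9.1.1 says may differ. In simulation a true stage-1 contrast of 0.30 fell to 0.17 with null stage-2 effects and to 0.04 with opposite ones. Adding A2 gave 0.30 in the opposite-effects case.

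**Conclusion.** The concern holds and should be fixed. The omission is plain from the text, and it conflicts with the SAP's own model in 9.2. The rank of 42 out of 47 rests on A3 = 0 for responders, which SAP 5.1 and 7.2.1 support. The −c(s_k − s_l)/3 shift is algebra under even allocation; only its size depends on the assumed carry-over. The harm falls on stage-2 contrasts and, more heavily, on the regimen comparison, where differences due to the first treatment are recovered at anywhere from under a tenth to just over half of truth. The tested interactions lose at most about 10% in the scenarios examined, and nothing if only main effects persist. The deep-phenotyping model inherits the same form.

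**What to change.** Rewrite the T4 equation in SAP 9.1.1, and through it 9.1.2, before database lock:

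- In the responder bracket, replace A3 by A2.
- In the non-responder bracket, keep A3 and add A2 with one reference arm dropped. Do not substitute one for the other.
- State that A3 = 0 for T3 responders, and enter the main effect of sex once.
- Add A2×Z2 to the T4 equation as a sensitivity analysis for persisting interactions.

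The count becomes 47 − 1 (sex) + 3 (A2 among non-responders) = 49 columns, with rank 49. If an intercept is added and only randomised patients are analysed, one further level must be dropped.

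Cost: no new data. Power for `psi_2` is 83% with or without A2. The standard error of a stage-2 contrast rises from 0.152 to 0.162, about 7%. The A2×Z2 model costs about 5 points of power if nothing persists (83% to 78%), is neutral at 50% carry-over (78% for both), and gains about 5 points at 100% (73% to 78%).

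Two smaller items can go in the same amendment. SAP 11 should point to 9.1.1, since 10.1.1 defines serious adverse events. Indicators for each patient's set of eligible treatments should join X2, because Protocol 8.1 lets allocation probabilities depend on eligibility. The second item affects arm main effects and regimen contrasts only; its size is unknown because no ineligible share is given.

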## Statistical Analysis Plan

phenotype. To address this aim, null hypothesis of regression coefficients will be used. We will use two-sided Wald tests to assess whether the hypothesized differential treatment responses are consistent with the clinical trial data. Let  $\theta$  denote a treatment-phenotype interaction (i.e., one of the elements of  $\psi_2$ ). The Wald test statistic testing  $H_0: \theta = 0$  is given by  $W = \frac{\theta}{SE(\theta)}$ . We will reject the null hypothesis at approximately the 95% level when  $|W| \geq 2$ .

### 9.1.2 Deep Phenotyping Analysis

A second analysis will assess whether deep-phenotyping measures are also predictive of differential treatment response. The form of the model will be nearly identical to the light phenotype-based primary analysis above. The analytic plan and strategy for performing inference on model parameters is the same as stated above in 9.1.1. The primary difference between the primary and secondary analysis is the number of treatment modifiers that were proposed by investigators. As a result, the deep phenotyping-based model will include multiple treatment-phenotype interaction terms for each treatment arm (see Table 5). *Table 5 Hypothesized differential responses to treatment*

Deep Phenotype variable	Measurement Modality	Expected treatment-phenotype interaction	Mechanistic Role
Subgenual ACC activity	fMRI	MBSR	Moderator
Ventrolateral PFC activity	fMRI	MBSR	Moderator
S1 activity	fMRI	MBSR	Moderator
Thalamus activity	fMRI	MBSR	Moderator
Baseline activity	Actigraphy	PT/Exercise	Moderator
Parasympathetic tone	Heart Rate Variability	PT/Exercise	Moderator
Vagal Tone	ECG and PPG	PT/Exercise	Mediator
High Basal Inflammation	Blood Sample	PT/Exercise	Moderator
Pain Threshold	QST	Acupressure	Moderator
Posterior Insula Glutamate	H-MRS	Acupressure	Moderator
Insula-DMN connectivity	fMRI	Acupressure	Moderator
DMN-SI connectivity	fMRI	Acupressure	Moderator
Deficient Lower Back Pain Inhibition	QST	Duloxetine	Moderator
Lesser PAG-Insula connectivity	fMRI	Duloxetine	Moderator
Elevated Stimulated inflammatory response	Blood Sample	Duloxetine	Moderator

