## 5.6 Study Assessments

Table 1 shows the schedule of assessments for screening, demographic data, outcomes, and light and deep phenotyping. Measurements at T2-T5 may occur within a target observation window around each nominal study sample time ( $\pm 2$  weeks). A subset of 160 eligible subjects enrolled in the clinical trial will undergo deep phenotyping.

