## 6 Sample Size

The study aims to continue randomizing patients with cLBP to initial treatment until 102 randomized patients per group are available for the analysis (i.e. completed their T1-T4 visits and had PGIC $\geq$ 2 at T2). This is the target patient group. Based on assumed attrition rates we expect the total number of consented patients to be over 500. Attrition rates include patients who are not randomized because their pain was “very much improved” after run-in (PGIC=1 at T2). Such patients will still be included in the analysis with their limited data. The power analysis, however, excludes these patients because effects in the randomized participants are of primary interest. The smaller subgroup based on 40 patients will be from the target patient group for deep phenotyping for specific treatments.

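### The deep-phenotyping model uses uncorrected robust errors on 160 patients, so each interaction test in the planned joint model runs at about 8–9% error rather than about 5%

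*SAP*

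**What the plan says.** SAP 9.1.1 sets the inference for the light model. It fits T3 and T4 pain interference jointly by "generalized estimating equations (GEE) with a working independence covariance matrix through the R package" gee, and adds: "We will use robust standard errors for variance estimation to account for the use of repeated measures". On testing it says "We will use two-sided Wald tests to assess whether the hypothesized differential treatment responses are consistent with the clinical trial data", and then: "We will reject the null hypothesis at approximately the 95% level when" |W| is at least 2. If the joint-modelling assumptions fail, the analysis falls back to stage 1 data only.

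SAP 9.1.2 moves this to the deep model without change: "The analytic plan and strategy for performing inference on model parameters is the same as stated above in 9.1.1". Table 5 lists 15 deep phenotypes: 4 for MBSR, 4 for PT/exercise, 4 for acupressure and 3 for duloxetine. SAP 5.6 gives the sample: "A subset of 160 eligible subjects enrolled in the clinical trial will undergo deep phenotyping". SAP 6 works with 40 patients per treatment. Neither 9.1.1 nor 9.1.2 names a small-sample variance correction or a t reference.

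**The concern.** A sandwich variance is built from squared residuals. When many coefficients are fitted to few patients, the fit absorbs part of each residual, and the uncorrected sandwich is too small. From the light to the deep analysis the sample falls from 408 to 160, while the hypothesized interactions rise from 8 to 15, each with a main effect and, in the joint model, stage-specific terms.

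Two things are at stake. The tests would flag moderators more often than the stated level allows. The confidence intervals, which SAP 7.5 prefers to p-values, use the same standard errors and would be too narrow.

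**Working it through.** **The plan's own figure.** The two-sided normal tail beyond 2 is 4.55%, which agrees with the SAP's approximate 5%. It is a large-sample figure.

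**Parameter count, stage 1 (T3) equation.**
- Baseline columns: sex, age, BMI, race, education and the T2 outcome. This is 6 columns if race and education are binary and 8 if each has three levels. The SAP does not give the coding, so it is an assumption.
- Treatment indicators: 4.
- Deep phenotypes: 15 main effects and 15 interactions.
- Total: 8 + 4 + 15 + 15 = 42 (40 with binary coding).

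**Parameter count, joint T3 and T4 model.** The T4 equation adds stage-specific terms. Responders contribute 1 treatment column (they are not re-randomized) and 15 phenotype columns. Non-responders contribute 4 and 15. Total: 42 + 1 + 15 + 4 + 15 = 77, on 160 patients with two records each.

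**Simulation.** Trials were generated with no true interactions, four equal arms, normal errors of constant variance and the SAP mean model. They were fitted under working independence with the uncorrected sandwich and tested at |W| ≥ 2. There were 2,000–3,000 trials per setting with 15 tests each. A separate GEE implementation (400 trials per model) gave 10.2% for stage 1 and 9.0% for the joint model.

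| Model | Patients | Parameters | Error per test |
|---|---|---|---|
| Joint T3 + T4 | 160 | 77 | 8.1–9.0% |
| Joint T3 + T4 | 136 | 77 | 9.2–9.6% |
| Joint, stage-specific terms reduced | 160 | 43 | 7.3% |
| Stage 1 | 160 | 42 | 10.2% |
| Stage 1, binary race and education | 160 | 40 | 9.9% |
| Stage 1, four-level race and education | 160 | 44 | 10.4% |
| Stage 1, skewed modifiers | 160 | 42 | 11.2% |
| Stage 1 | 136 | 42 | 11.6% |
| Light model, T3 equation | 408 | about 28 | 5.9% |

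The joint range covers responder shares of 15–40%, T3–T4 correlations of 0.5 and 0.7, skewed modifiers, and 15% of T4 records missing. The 136-patient rows are 160 × 0.85, because SAP 7.4 expects no more than 15% missing data.

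**Check by hand.** The robust standard error averages about 0.88 of the true one in the joint model and 0.84 in stage 1. A cut-off of 2 then acts like 2 × 0.88 = 1.76 and 2 × 0.84 = 1.68. The normal tails beyond these are about 7.8% and 9.3%. Sampling variation in the standard error accounts for the rest.

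**Coverage.** 100 − 9.0 = 91.0% to 100 − 8.1 = 91.9% in the joint model; 100 − 10.2 = 89.8% in stage 1.

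**Cause.** In stage 1, model-based standard errors with the same cut-off of 2 give 4.7%. With 160 − 42 = 118 residual degrees of freedom the t cut-off would be 1.98, so 2 is not too lenient.

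**Corrections tried.** Joint model: CR2 with a t reference 4.9%; the more conservative Mancl–DeRouen correction with |W| ≥ 2, 2.8%. Stage 1: HC2 with t 5.8%; HC1 with t 6.2%; HC3 with t 2.5%.

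**The case against.** **The error rate does not double in the planned analysis.** A reader might infer from the 42-parameter equation that the planned tests run at twice their level. The SAP does not support that. Stage 1 alone is the fallback, and the joint model comes to 1.6–1.8 times 5% at 160 patients.

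**Robust errors may not apply in the fallback.** The SAP justifies them by the repeated measures, and with one record per patient that reason is gone. SAP 9.1.1 also assumes normality for inference. If model-based errors were used, the level would be about right under constant variance. This stands: the 10% figure is conditional on keeping robust errors, and the SAP does not say which errors apply.

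**The cut-off is not to blame.** A reader might fault |W| ≥ 2. The model-based result above rules that out.

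**The analysis is a screen.** SAP 7.5 declines multiplicity control, presents intervals and effect sizes, and aims at combinations for future study. Treating 15 tests as independent, the chance of at least one false positive is already 1 − 0.95^15 = 54% at an exact 5%; at 8.5% it is 1 − 0.915^15 = 74%. Expected false positives rise from 15 × 0.05 = 0.75 to 15 × 0.085 = about 1.3. This limits the harm but does not remove it. Accepting 15 uncorrected tests is not accepting a wrong level for each, and the intervals reported instead rest on the same errors. Cross-validation, promised where appropriate, does not repair an interval.

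**Aim 3 does not rest on these tests alone.** A reader might infer that it does. The protocol also plans imaging regressions and cross-validated SVM with label permutation (10.2), and regularized models with cross-validated AUC (18.1.5). These do not depend on the GEE standard errors.

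**Conclusion.** The concern holds for SAP 9.1.2. As written, the stated level is not met: about 8–9% per test in the planned joint model, and about 10% in the stage 1 fallback if robust errors are kept (11–12% with 15% of patients lost). Intervals at a nominal 95% cover about 90–92% with all 160 patients. The uncorrected sandwich variance is the cause, and the light model needs no change on this account.

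The exact size rests on assumptions the documents do not settle: race and education at three levels each, the responder share at T3, the T3–T4 correlation and the modifier distributions. Inflation appeared in every setting tried, and the lowest figure (7.3%) came from a joint model with fewer stage-specific terms than the SAP writes. A full 160 is also optimistic, because all 15 measures enter one model and the protocol excludes scans for head motion (10.2.1) and poorly fitted spectroscopy values (10.2.2).

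**What to change.** Add a sentence to SAP 9.1.2 along these lines: for the deep model, inference on the joint T3 and T4 fit will use a bias-reduced cluster-robust variance (CR2 type) with a t reference in place of |W| ≥ 2. If the analysis falls back to stage 1, it will use HC2 standard errors with a t reference, or model-based errors if constant variance is tenable. Apply the same standard errors to the intervals reported under SAP 7.5.

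No new data or patients are needed. It may require an R package other than gee. Intervals become about 14–22% wider, with correspondingly lower power.
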